11.1.4.1 Complete Response (CR)

Disappearance of all target and non-target CT/MRI lesions.

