11.1 Response Criteria for CT/MRI Lesions

For lesions evaluated by CT/MRI, this study will use the definitions of measurable disease from the Response Evaluation Criteria in Solid Tumors (RECIST 1.1; European Journal Cancer 45: 228-247, 2009) modified per the criteria below to define target lesions (lesions which are measurable AND evaluable for response).

11.1.1 Definition of soft tissue TARGET LESIONS on CT/MRI:

Soft tissue target lesions that will be followed for response must meet criteria in a. and b. below:

- a. A target lesion must be measurable, defined as a soft tissue lesion that can be accurately measured in at least one dimension with a longest diameter $\geq 10\text{mm}$, or for lymph nodes $\geq 15\text{mm}$ on short axis. (The short axis is measured after identifying the longest diameter of a lymph node or nodal mass, and then measuring the longest perpendicular diameter to that as the short axis).
- b. A target lesion must also be evaluable for response: To be evaluable, the lesion must also be MIBG or FDG-PET avid (if tumor known to be MIBG non-avid), or have a biopsy as required in the eligibility criteria. If one soft tissue lesion present at enrollment is biopsied showing neuroblastoma or ganglioneuroblastoma at any time point, then all other soft tissue lesions present at enrollment are considered evaluable. Bone marrow positivity does not affect soft tissue evaluability.

NOTE: Soft tissue components of bone lesions will be considered measurable lesions if $> 10\text{mm}$ in at least one dimension, and evaluable for response if MIBG avid (or FDG-PET-avid if tumor known to be MIBG non-avid).

Serial measurements of target lesions are to be done with the same method of assessment (either CT or MRI) used to characterize each lesion reported at baseline. The sum of diameters (longest for non-nodal lesions, short axis for nodal lesions) for all target lesions will be calculated and reported as the **sum of diameters**.

11.1.2 NON-TARGET SOFT TISSUE LESIONS will include:

- a. Leptomeningeal tumor and tumor in cerebrospinal fluid cytology will be considered non-target lesions.
- b. Lesions that are considered likely to be active tumor by the treating physician based on clinical correlation (for example, hepatic and pulmonary nodules)

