11.1.3 The following lesions will NOT be followed to evaluate response either as target lesions or non-target lesions, if they meet the criteria below **AND** the treating physician feels they are unlikely to represent active tumor (an exception for active tumor will be made for c. below):

- a. Measurable soft tissue lesions ($\geq 10\text{mm}$) that are not MIBG avid or PET avid (if tumor known to be MIBG non-avid) and if biopsied did not show neuroblastoma or ganglioneuroblastoma.

- b. Non-measurable soft tissue lesions < 10mm or non-measurable lymph nodes (defined as lymph nodes >10 to <15mm on short axis).
- c. Intramedullary bone lesions will not be followed for CT/MRI response even though they are felt to represent active tumor since they will be evaluated with MIBG scans (or FDG-PET scans if MIBG non-avid), and since bone changes on CT/MRI are known to persist after resolution of active tumor.

11.1.4 The response of the CT/MRI lesions will be defined as outlined below:

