11.1.4.2 Partial Response (PR)

At least a 30% decrease in sum of diameters of CT/MRI lesions (using longest diameter for non-nodal lesions and short axis for nodal lesions), taking as reference the measurement of target lesions performed at study enrollment. Non-target CT/MRI lesions must be stable to smaller in size. No new lesions. MIBG (FDG-PET for MIBG non-avid tumors) uptake may still be present in lesions positive at enrollment.

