11.6.1 Complete Response (CR)

Response of CR or NI for MIBG, (FDG-PET if tumor is not MIBG avid), CT/MRI, and bone marrow.

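### CT/MRI complete response gives no short-axis limit for lymph nodes, so a node that shrinks to 10 mm or less but stays visible may be graded PR instead of CR

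*Combined protocol and SAP*

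**What the plan says.** Section 11.1.1 makes a node a target at a short axis of 15 mm or more and sets how nodes are counted: "The sum of diameters (longest for non-nodal lesions, short axis for nodal lesions) for all target lesions will be calculated". The PR rule in 11.1.4.2 repeats this ("using longest diameter for non-nodal lesions and short axis for nodal lesions"), and the PD rule in 11.1.4.3 does the same. The CR rule in 11.1.4.1 does not separate nodes from other lesions. It reads "Disappearance of all target and non-target CT/MRI lesions".

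The only lower bound on nodal size is in 11.1.3(b), on lesions that are not followed: "non-measurable lymph nodes (defined as lymph nodes >10 to <15mm on short axis". RECIST 1.1 is brought in for a limited purpose ("this study will use the definitions of measurable disease from the Response Evaluation Criteria in Solid Tumors", modified by the protocol). The response categories themselves are written out in 11.1.4.

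Overall CR under 11.6.1 needs "Response of CR or NI for MIBG, (FDG-PET if tumor is not MIBG avid), CT/MRI, and bone marrow". Section 10.2.2 lists CR, VGPR and PR as separate categories and counts all three as responders; CR-MRD is not in that list. Section 11.0 has sites and central review apply the same criteria, with central review final for the analysis.

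**The concern.** Nodes have their own measure in target selection, in the sum, in PR and in PD, but not in CR. On the protocol's own scale a node of 10 mm or less falls below even the non-measurable band. Yet if it can still be seen on the scan, a literal reader will say that it has not disappeared. The grade between CR and PR then turns on whether the disease was nodal and on how the reader takes an undefined word.

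At stake is the split of best response (10.6.2) between CR or CR-MRD and PR. For patients whose only CT/MRI disease is non-target, responder status itself is at stake.

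**Working it through.** **Design figures.** Section 10.4 gives a 90% chance of at least 1 response in 14 at a true rate of 15%. Recomputed: 1 − 0.85^14 = 0.897. It gives a half-width of no more than 0.24 at 20 patients. The exact two-stage interval, stopping at 0 of 14, has a largest half-width of 0.228, at 10 of 20. Both agree, and neither depends on how CR and PR are divided.

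**Step 1: does a shrunken target node reach PR?** Inputs: entry short axis of at least 15 mm (11.1.1), end value of at most 10 mm (lower edge in 11.1.3(b)), PR at a 30% decrease (11.1.4.2).
- Decrease = (entry − end) / entry.
- Smallest case: (15 − 10) / 15 = 33.3%.
- Example: (18 − 7) / 18 = 61.1%.
- If non-nodal targets also vanish, the sum falls by a larger fraction.

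So, with no new lesions and non-target lesions stable or smaller, CT/MRI is at least PR. Read literally, it is not CR.

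**Step 2: what happens to the overall grade?** Apply 11.6 and the table in 11.6.10 with CT/MRI as PR and then as CR. CT/MRI CR requires that every other CT/MRI lesion has gone.

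| MIBG | Marrow | Overall if CT/MRI is PR | Overall if CT/MRI is CR |
|---|---|---|---|
| CR or NI | CR or NI | PR | CR |
| CR or NI | CR-MRD | PR | CR-MRD |
| CR or NI | SD, 5% or less at entry | PR | Minor response |
| CR or NI | SD, above 5% at entry | Minor response | Minor response |
| PR | CR, CR-MRD, NI, or SD with 5% or less at entry | PR | PR |
| PR | SD, above 5% at entry | Minor response | Minor response |
| SD | CR, CR-MRD, NI or SD | Minor response | Minor response |

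The first two rows carry the point. The third shows a separate gap: 11.6.3 needs PR in CT/MRI or MIBG, so a patient with CR in CT/MRI, CR or NI in MIBG, and low-level stable marrow disease has no PR row. The better CT/MRI grade gives the worse overall grade.

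**Step 3: size.** One patient in 20 is 1/20 = 5 points of the CR rate. In the first two rows the patient is PR under the current wording, hence already a responder, so CR plus PR is not reduced.

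**Step 4: non-target nodes.** A node judged likely to be active tumor can be followed as non-target (11.1.2(b)). If the patient has no target lesions and the node shrinks but stays visible, CT/MRI is SD-NTL (11.1.4.5). With MIBG CR and marrow NI or CR:
- CR fails, because 11.6.1 needs CT/MRI CR or NI.
- PR fails, because neither CT/MRI nor MIBG is PR.
- SD fails, because 11.6.5 does not admit a CR in another parameter.
- Minor response applies only if SD-NTL is taken as stable disease; otherwise no category fits.

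Either way the patient is not among the responders in 10.2.2. With marrow CR-MRD, the table in 11.6.10 accepts SD-NTL and gives CR-MRD, while the text of 11.6.2 does not accept it.

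**The case against.** The best case for the current text has four parts.

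- **The word is open.** If a node of 10 mm or less is not a lesion on the protocol's scale, then a node that falls to 7 mm has ceased to be one, and CR is met. This stands in part: a reader might infer that nodal complete responses are always graded PR, and the documents do not support that. But 11.1.3(b) decides which lesions are followed, depends on the physician judging active tumor unlikely, and does not say when a target node has gone. The sound statement is that PR may be assigned and readers may differ.
- **The strictness may be intended.** Version 1.1 in Appendix VIII asked only that target lesions disappear, with non-target lesions stable or smaller; version 1.2 adds non-target lesions. That is a fair reading of the revision, but it does not explain the absence of a nodal rule.
- **The anatomical premise is outside the documents.** They do not say that treated nodes shrink to normal size and stay visible. This is general knowledge and is used here as an assumption. The 10 mm is the protocol's own lower edge, not a response threshold that it states.
- **No planned decision uses the CR rate.** Aim 1.4, the Stage 1 rule and the confidence interval use objective response, and the *AURKA* analysis in 10.8 uses PR or better. This stands and keeps the point small.

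A reader might also infer that every patient with a nodal target loses a CR. That is too broad: the shift needs all other CT/MRI lesions gone, MIBG CR or NI, and marrow CR, NI or CR-MRD.

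**Conclusion.** The gap is real and minor. Under the literal rule a target node that reaches 10 mm or less but remains visible may hold CT/MRI at PR. In the first two rows of the table it then holds best overall response at PR instead of CR or CR-MRD. Each such patient is 5 points of the CR rate at 20 patients; the documents do not say how many patients have nodal targets, and the number could be zero.

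For target nodes the current wording does not lower CR plus PR. It would be wrong to conclude that the response rate is safe in every case: a patient with only non-target CT/MRI disease who is left at SD-NTL, with MIBG CR and marrow NI or CR, is outside both CR and PR. It would be equally wrong to read this as a general bias in the primary endpoint. The sample size and the Stage 1 rule do not change; the count that enters the rule could differ only through that non-target route.

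**What to change.** Make these edits together and apply them at central review:

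1. In 11.1.4.1, state that nodal target and non-target lesions must reach a short axis of 10 mm or less and that all other lesions must disappear.
2. In 11.6.3 and the table in 11.6.10, add a PR row for CT/MRI CR with MIBG CR or NI and marrow SD with 5% or less at entry.
3. In 10.2.2, add CR-MRD to the responder categories.

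The first edit should not go in alone. Without the second, it would move the third row of the table from PR to Minor response. Without the third, it would move patients into a category that the responder list omits. Either would take a patient out of the responders because of a better CT/MRI grade.

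The cost is a few sentences and a re-reading of nodal measurements. Short axes of target nodes already enter the sum of diameters; those of non-target nodes can be read from existing scans. No extra imaging or patients are needed.

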11.1.4.2 Partial Response (PR)

At least a 30% decrease in sum of diameters of CT/MRI lesions (using longest diameter for non-nodal lesions and short axis for nodal lesions), taking as reference the measurement of target lesions performed at study enrollment. Non-target CT/MRI lesions must be stable to smaller in size. No new lesions. MIBG (FDG-PET for MIBG non-avid tumors) uptake may still be present in lesions positive at enrollment.

11.1.4.3 Progressive Disease (PD)

At least a 20% increase in sum of diameters of target lesions (using longest dimension for non-nodal lesions and short axis for nodal lesions) taking as reference the smallest sum of diameters while on study (this includes the baseline if that is the smallest on study). In addition to the relative increase of 20%, the sum must also demonstrate an absolute increase of 5mm. A new target or non-target tumor lesion seen on CT/MRI without MIBG or PET uptake is considered PD, but may be biopsied to rule out PD. An overall substantial worsening of non-target CT/MRI lesions is also considered as a criteria for PD (guidance for substantial includes a 73% increase in volume, or sufficient worsening of overall non-target disease such that the treating physician feels a change in therapy is indicated).

New uptake of MIBG (or FDG-PET for MIBG non-avid tumors) at target and/or non-target lesions which are stable in size, will be captured in MIBG response (or FDG PET response if tumor is MIBG non-avid) and will NOT be graded as CT/MRI progression (CT/MRI would be graded as SD). Biopsy of such lesions can be done to rule out PD for the MIBG (or FDG-PET) response.

11.1.4.4 Stable disease (SD)

(Applies only to patients with target lesions)

Neither sufficient shrinkage in sum of diameters to qualify for PR and patient does not meet any criteria for PD. No new lesions. Non-target lesions must be stable to smaller in size.

11.1.4.5 Stable disease-no target lesions (SD-NTL)

(Applies to patients with non-target lesions only)

Non-target lesions are still present; may be smaller or stable in size, and do not meet criteria for PD. No new non-target tumor lesions (new lesions may be biopsied to rule out PD).

11.1.4.6 Not involved (NI): No target or non-target lesions

11.1.4.7 Non-target lesions only: Patient has no target lesions, but does have non-target lesions.

11.1.4.8 Not evaluable (NE)

CT/MRI scans are of inadequate quality as assessed by central reviewer, or scans are not repeated of all lesions with tumor documented at entry. (Note that patients not evaluable at a given time point may be evaluable for response at later time points if all scans done with adequate quality at later time point.) or if based on Study Management Committee / PI review it is deemed that there is insufficient data to grade response.

11.1.4.9 Not done (ND)

No CT/MRI scans were done at the given time point.

11.2 Response Criteria for Morphologic Bone Marrow Disease

Routine morphology (with or without routine immunocytochemistry) will be used for baseline evaluation and all subsequent response evaluations performed while on protocol therapy, and at end of protocol therapy. Central review will be performed on bilateral biopsies only, unless tumor is seen only on aspirates.

Patients with $\leq 5\%$ tumor on all samples of the bilateral bone marrow aspirate and biopsies at study entry will be evaluable for bone marrow response, but defined separately from patients with $> 5\%$ at study entry.

The percentage of tumor in an aspirate will be calculated as the number of tumor cells divided by the number of total nucleated cells. The percentage of tumor in a biopsy will be calculated as the percent of tumor cells (including neuroblasts, mature and maturing ganglion cells) based on the bone marrow parenchymal surface area examined (excluding Schwannian stroma).

11.2.1 Complete Response (CR)

Greater than 5% tumor cells seen on any one sample of bilateral aspirates/biopsies performed at study entry, with no tumor cells seen on bilateral aspirates and biopsies at one subsequent time point.

11.2.2 Complete Response Minimal Residual Disease (CR-MRD) Percentage of tumor $\leq 5\%$ on all samples of bilateral aspirates/biopsies at study entry, with no tumor cells seen on bilateral aspirates and biopsies at one subsequent time point after starting protocol therapy. If subsequent time points remain negative, then patient is classified as CR-MRD. If subsequent time points are intermittently positive but with $\leq 10\%$ tumor, then response should be reclassified as SD at the negative time points initially reported as CR-MRD.

11.2.3 Progressive Disease (PD)

Patients with any amount of tumor in the bone marrow at study entry will be considered to have PD if one subsequent evaluation shows $>10\%$ tumor on any one bone marrow sample AND there is a doubling in the amount of tumor compared to study entry (baseline).

For example a patient entering with $\leq 5\%$ tumor in marrow must increase to $> 10\%$ tumor to have PD; a patient entering with 30% tumor must increase to $\geq 60\%$ tumor. If patients have an increase in tumor amount which is less than the amount specified for PD, the response will be classified as SD.

Patients who enter on study with no tumor seen will be considered PD if ONE subsequent evaluation shows $>10\%$ tumor. If $\leq 10\%$ tumor is seen on one subsequent evaluation or intermittently, the response will be classified as SD.

11.2.4 Stable Disease (SD)

Stable disease will be defined as persistence of an amount of tumor in the bone marrow that does not meet criteria for progressive disease or CR or CR- Minimal Residual Disease. (Note that patients who enter with $\leq 5\%$ tumor and have one negative bone marrow which is initially graded as a CR-MRD and then on subsequent time points have 1-10% tumor noted would be then considered as SD at all time points, including the time point initially graded as CR).

11.2.5 Not Evaluable (NE)

Patients for whom follow-up bone marrows do not include an attempt to obtain bilateral aspirates and biopsies and do not have at least one adequate biopsy sample, as assessed by local site's pathology report for that time point or if based on Study Management Committee / PI review it is deemed that there is insufficient data to grade response.

11.2.6 Not involved (NI)

Patients with no evidence of neuroblastoma in the bone marrow at study entry, and remain negative on subsequent evaluations. (Note that such patients may be reclassified as SD if they meet the SD criteria above with intermittent tumor in the bone marrow).

11.2.7 Not done (ND)

Bone marrow evaluation not done at a given time point.

[figure not shown]
11.3. Response Criteria for MIBG Avid Lesions

MIBG response will be graded using a modification of the Curie scoring scale (Eur J Cancer 1995;31A:256-261). The treating site will report the MIBG response using Curie, however the statistical endpoint of MIBG response will utilize the Curie score from the central reviewer.

MIBG scans will be scored for 10 regions; 9 anatomic regions for skeletal metastases, and a 10th region for any MIBG avid soft tissue disease.

Each of the 10 regions will be given a score of 0-3, as defined below.

Scoring of Skeletal Disease Regions 1 – 9	
Scoring	MIBG uptake
0	No MIBG uptake
1	1 focal lesion
2	> 1 focal lesion
3	> 50% of a region

The **absolute extension score** is obtained by adding the scores of all ten regions. The presence of a MIBG avid lesion, and NOT the “intensity” of MIBG-avidity, determines the scoring within a particular region.

REGIONS 1 – 9 / SKELETAL DISEASE: Cranio-facial disease is scored in Region 1, cervico-thoracic spine in Region 2, ribs / sternum / clavicles / scapula in Region 3, lumbar-sacral spine in Region 4, pelvis in Region 5, humeri in Region 6, distal upper extremities in Region 7, femurs in Region 8, and distal lower extremities in Region 9 (see figure below).

REGION 10 / SOFT TISSUE DISEASE: Soft tissue disease within the neck, chest or abdomen/pelvis is scored within Region 10. Examples of soft tissue lesions may include MIBG avid cervical, paraspinous, adrenal, renal, retroperitoneal, or hepatic masses.

SCORING SOFT TISSUE DISEASE: Score = 1 indicates an isolated soft tissue mass that encompasses < 50% of that region (chest or abdomen/pelvis). Score = 2 indicates > 1 soft tissue lesion in the neck, chest or abdomen/pelvis. A soft tissue score = 3 indicates MIBG avid soft tissue disease that encompasses > 50% of either the chest or abdomen/pelvis. (For example, a large adrenal mass in which the MIBG avidity encompasses > 50% of the abdomen/pelvis is scored a 3 for Region 10). Cervical soft tissue disease is included in the chest region.

If no MIBG-avid soft tissue lesions are present, then score 0 for Region 10.

If a solitary soft tissue lesion extends into both the chest and abdomen/pelvic regions, score 3 for that lesion. For example, a large paraspinous mass that extends along the thoracic and lumbar spine would be scored a 3 for Region 10. Any corresponding metastatic bone disease within the thoracic or lumbar spine would be scored separately for the cervico-thoracic spine (Region 2) and lumbar spine (Region 4).

Conjugate planar imaging will be used to score a given region. SPECT scans may be used as an adjunct, but only to help delineate the location of the MIBG avid lesion.

The **relative score** is calculated by dividing the absolute score at each time by the corresponding pre-treatment overall score. The relative score of each patient is calculated at each response assessment and classified as below:

- a. Complete response: all areas of uptake on MIBG scan completely resolved.
- b. Partial response: Relative score ≥ 0.1 to ≤ 0.5
- c. Stable disease: Relative score > 0.5 to < 1.2
- d. Progressive disease: New lesions on MIBG scan OR a relative score ≥ 1.2 . Biopsy of new lesions may be done to rule out progressive disease. If biopsy is negative for tumor (neuroblastoma and/or ganglioneuroblastoma), patient will not meet definition of PD.
- e. Not evaluable (NE): MIBG scan of inadequate quality as assessed by central reviewer.
- f. Not involved (NI): No MIBG avid lesions at study entry and subsequent response time points.
- g. Not done (ND): MIBG scan not done at a given response time point

11.4 Response Criteria using FDG-PET scans (for MIBG non-avid patients)

Patients known to be non-avid for MIBG should have FDG-PET scans performed for monitoring response. FDG-PET avid lesions will be scored by the presence or absence of a lesion with uptake that is two times above background.

11.4.1 Complete response (CR)

Resolution of all FDG-PET uptake in all FDG-PET avid lesions identified at baseline and no new FDG-PET avid lesions.

11.4.2 Partial response (PR)

Reduction of number of lesions by FDG-PET by $> = 50\%$. No new FDG-PET avid lesions.

11.4.3 Stable disease (SD)

Changes that do not meet the criteria for PR or PD.

11.4.4 Progressive disease (PD)

New lesions on FDG-PET scan. Note: biopsy may be done to exclude causes of FDG-PET uptake other than tumor. If biopsy is negative for tumor (neuroblastoma and/or ganglioneuroblastoma), patient will not meet definition of PD.

11.4.5 Not evaluable (NE)

FDG-PET scan of inadequate quality to evaluate response or if based on Study Management Committee / PI review it is deemed that there is insufficient data to grade response.

11.4.6 Not involved (NI)

No FDG-PET uptake that is two times above background.

